### **9.4. Secondary Endpoint**

- **Overall survival (OS) rate**, measured from the date of starting therapy to the date of death from any cause. Patients alive and patients who are lost to follow up at the time of the final

analysis will be censored at the date of the last contact. The minimum follow-up time required for OS assessment for all patients will be 2 years.

- **Progression-free survival (PFS) rate**, measured from the date of starting therapy to the date of disease progression, relapse or death from any cause. Responding patients and patients who are lost to follow up will be censored at their last assessment date. Patients who will have no tumor assessment after the start of therapy due to interruption of both drugs will be considered failures at the date of treatment interruption in the PFS analysis. The minimum follow-up time required for PFS assessment for all patients will be 2 years.
- **Treatment safety** through the measurement of: patients' withdrawal rate, incidence, type and grade of any adverse event (AE) and serious adverse event (SAE), hospitalization rate throughout the study, and patients' compliance to oral treatment.

## 10. STUDY DESIGN

### 10.1. Overview of study design

This is a prospective, multicenter, single arm, phase II study.

Patients with histologically confirmed FL, in need of a systemic approach and failing (i.e. with refractory disease [no response or response lasting less than 6 months] or with a proven disease relapse) at least 2 previous lines of treatment, including any antibody directed against the CD20 antigen-containing chemotherapy, will undergo a combined treatment of obinutuzumab and idelalisib.

After providing written informed consent, patient will be evaluated for eligibility during a 28-day screening period. In the meanwhile, their bioptic samples will be submitted to the central laboratory designed by FIL to undergo central diagnosis review. If they continue to meet eligibility criteria, they will start the obinutuzumab plus idelalisib regimen and PJP prophylaxis. Histological centralized review is compulsory for treatment start, but the local pathology report is sufficient for patient enrollment.

Obinutuzumab will be administered intravenously at a flat dose of 1000 mg on day 1, 8, 15 of the first cycle, then repeated on day 1 of each subsequent cycle, for a total of 6 cycles (each cycle is completed in 28 days). Idelalisib will be given continuously on a daily 150 mg bid schedule (24 weeks).

If one of the two drugs has to be permanently discontinued due to any cause, patient may continue treatment with the other agent if it is judged to be a clinical benefit.

For patients achieving at least a partial response at the end of induction, a maintenance phase with obinutuzumab is scheduled (on day 1 every two months for two years or until progression or unacceptable toxicity, whichever comes first).

Patients with a stable disease at EOI will enter a follow-up phase and will be followed with repeated CT scans every six months for two years or until progression or death. The same applies to patients in SD at EOT.

Patients with progressive disease, if progression is documented during induction or maintenance phase, are considered off-treatment, but will enter a survival follow up period of two years after treatment discontinuation and will be considered evaluable for OS till study end.

If progression is documented during follow up period, patients will enter a survival follow up period until globally 2 years of follow up are achieved.

Patients who will interrupt therapy (for any reason), if at least in stable disease at time of treatment discontinuation, will enter the follow-up period and will be re-evaluated for response every 6 months for 2 years or until progression/start of new anti-lymphoma therapy/death. If these patients experience progression/start of new lymphoma treatment will be followed up for survival for a total of 2 years from treatment discontinuation. These patients are however considered evaluable for PFS and OS.

Non-responder, relapsing or progressive patients will be treated according to best clinical practice.

These patients are however considered evaluable for OS.

CT scans have to be performed at baseline, after induction cycle 3 and 6 (EOI), every 3 months during the first year of maintenance, every 4 months during the second year of maintenance, at the end of treatment after 2 years of maintenance or in case of early withdrawal (EOT), at relapse/progression and during follow-up.

PET scans are mandatory at baseline, after induction cycle 3 and 6 (EOI), at the end of treatment after 2 years of maintenance or in case of early withdrawal (EOT) and at relapse/progression. At all additional timepoints (including follow-up) they are optional and will be done at clinician discretion only if in accordance with center clinical practice.

## 10.2. Number of patients

A total of 43 patient will be enrolled in the study: 15 patients at the Stage 1 of the study.

If there are 9 or fewer responses in these 15 patients, the study will be stopped. Otherwise, 28 additional patients will be accrued for a total of 43 patients.

## 10.3. Duration of the study

Patients will be recruited over 1.5 year + 6 months of induction + 2 years of maintenance and followed for 2 years after the end of the treatment phase (6,5 years).

End of study is defined by the last visit planned by the protocol of the last patient in follow-up that means 2 years after the EOT visit (LPLV). The Final Study Report will be provided after the end of the Study.

# 11. STUDY POPULATION

## 11.1. Inclusion criteria

- Relapsed or refractory, histologically confirmed CD20-positive follicular non-Hodgkin's lymphoma, grade 1, 2 or 3A according to the WHO 2017 classification.
- Age  $\geq$  18 years.
- At least 2 prior systemic therapies for follicular lymphoma including both any antibody directed against the CD20 antigen and a chemotherapy combination.
- Treatment indications, with the presence of at least one of the following:
  - bulky disease (nodal or extranodal – except spleen – mass more than 7 cm in its greater diameter or involvement of at least 3 nodal or extranodal sites, each with a diameter equal to or greater than 3 cm);
  - at least one B-symptom (fever  $>$  38°C of unclear etiology, night sweats, weight loss greater than 10% of body weight in the prior 6 months);
  - symptomatic splenomegaly;
  - compression syndrome (i.e. of orbits, ureters, gastrointestinal tract, biliary tract);
  - lymphoma-related cytopenias (hemoglobin  $<$  10 g/dL and/or platelets  $<$  100·10^9/L and/or neutrophils  $<$  1.5·10^9/L);
  - pleural or peritoneal serous effusions.
  -
- Eastern Cooperative Oncology Group (ECOG) performance status (PS)  $\leq$  2.
- Adequate hematological function, unless abnormalities due to underlying disease, within 28 days prior to signing informed consent, defined as follows: neutrophils  $>$  1.5·10^9/L, platelets  $>$  75·10^9/L, hemoglobin  $>$  8,0 g/dL with transfusion independence.
- Capacity and willingness to adhere to study visit schedule and specific protocol procedures.
- Willingness to sign a written informed consent.
- Compliance with effective contraception without interruption, from 28 days before treatment start up to 18 months after treatment discontinuation (see paragraph 13.9), agreeing not to donate the semen during treatment and for 18 months after discontinuation (if the patient is male), or to undergo ongoing pregnancy test during the course of the study (if the patient is

female). Birth control methods considered acceptable for the study are those highly effective (IUS, hormonal methods, tubal sterilization, sexual intercourse with a vasectomized male partner) or effective (male condom, diaphragm, cervical cap). According to the usual lifestyle of the subjects, if they are not willing to adopt the prescribed contraceptive methods, they have to practice true abstinence for all the period above reported.

- Patients must agree to undergo JPJ prophylaxis throughout the treatment period and 2-6 months thereafter (before consulting with Medical monitor).

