## 15. STUDY PROCEDURES TIMEPOINTS

### 15.1. Screening period

within 28 days prior to Study Cycle 1 Day 1

All subjects will be screened for study eligibility including:

- Confirmed relapsed/refractory FL\*
  - \* *Histological centralized review is compulsory for start of treatment, but the local pathology report is sufficient for patient enrollment*
- Medical History;
- Physical Examination;
- Height, Weight;
- ECOG;
- Vital Signs;
- B symptoms;
- Hematology including Hemoglobin, Platelets, White blood cell count (WBC) with differential;
- Blood chemistry including creatinine, total bilirubin, LDH, AST, ALT, serum proteins with electrophoresis, immunoglobulin levels;
- Electrocardiogram;
- LVEF by either bi-dimensional echocardiogram or cardiac scintigraphy (MUGA);
- Measurable lesion assessment on CT scan of neck, chest, abdomen and pelvis, to be performed with and without contrast;
- FDG-PET scan (mandatory)
- Pregnancy test (if applicable);
- A bone marrow biopsy with immunohistochemical evaluation;
- Local molecular evaluation of BCL-2 rearrangement on marrow blood;
- Viral tests including HIV, HBsAg, HBsAb, HBcAb, HBV DNA and HCV (HCV RNA required for patient who are HCV antibody positive);
- Monitoring for CMV infection;
- Concomitant medications.

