## **17. STATISTICAL CONSIDERATIONS**

### **17.1. Sample size**

Optimal Simon's two-stage design [32] has been used to calculate the sample size.

The null hypothesis that the true response rate is 55% (response rate of idelalisib single agent) [6] will be tested against a one-sided alternative response rate of 75% (response of obinutuzumab in combination) [23]. Last available clinical response will be considered for patients who will permanently discontinue for any cause both drugs of the experimental combination before the completion of the 6th cycle (planned duration of induction phase).

For the first stage, the accrual will be suspended when 15 patients will have started experimental therapy. If there are 9 or fewer responses in these 15 patients, the study will be stopped.

Otherwise, enrollment will be reopened until 28 additional patients will start experimental therapy for a total of 43. The null hypothesis will be rejected if 29 or more responses are observed in 43 patients.

This design yields a type I error rate of 5% and power of 80% when the true response rate is 75%.

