**APPENDIX B: COMMON TERMINOLOGY CRITERIA FOR ADVERSE EVENTS (CTCAE)**

In the present study, adverse events and/or adverse drug reactions will be recorded according to the: **Common Terminology Criteria for Adverse Events (CTCAE), version 5.0**.  
Click on [CTCAE, version 5.0](#) to download the document in pdf.

**APPENDIX C: Response assessment by CT and PET scans**SOURCE: *Cheson et al., J Clin Oncol. 2014 Sep 20;32(27):3059-68 [28].*

Revised Criteria for Response Assessment		
Response and Site	PET-CT–Based Response	CT-Based Response
Complete	Complete metabolic response	Complete radiologic response (all of the following)
Lymph nodes and extralymphatic sites	Score 1, 2, or 3* with or without a residual mass on 5PS† It is recognized that in Waldeyer's ring or extranodal sites with high physiologic uptake or with activation within spleen or marrow (eg, with chemotherapy or myeloid colony-stimulating factors), uptake may be greater than normal mediastinum and/or liver. In this circumstance, complete metabolic response may be inferred if uptake at sites of initial involvement is no greater than surrounding normal tissue even if the tissue has high physiologic uptake	Target nodes/nodal masses must regress to $\leq 1.5$ cm in LDi No extralymphatic sites of disease
Nonmeasured lesion	Not applicable	Absent
Organ enlargement	Not applicable	Regress to normal
New lesions	None	None
Bone marrow	No evidence of FDG-avid disease in marrow	Normal by morphology; if indeterminate, IHC negative
Partial	Partial metabolic response	Partial remission (all of the following)
Lymph nodes and extralymphatic sites	Score 4 or 5† with reduced uptake compared with baseline and residual mass(es) of any size At interim, these findings suggest responding disease  At end of treatment, these findings indicate residual disease	$\geq 50\%$ decrease in SPD of up to 6 target measurable nodes and extranodal sites When a lesion is too small to measure on CT, assign 5 mm $\times$ 5 mm as the default value When no longer visible, 0 $\times$ 0 mm For a node > 5 mm $\times$ 5 mm, but smaller than normal, use actual measurement for calculation
Nonmeasured lesions	Not applicable	Absent/normal, regressed, but no increase
Organ enlargement	Not applicable	Spleen must have regressed by > 50% in length beyond normal
New lesions	None	None

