\*A score of 3 in many patients indicates a good prognosis with standard treatment, especially if at the time of an interim scan. However, in trials involving PET where de-escalation is investigated, it may be preferable to consider a score of 3 as inadequate response (to avoid undertreatment). Measured dominant lesions: Up to six of the largest dominant nodes, nodal masses, and extranodal lesions selected to be clearly measurable in two diameters. Nodes should preferably be from disparate regions of the body and should include, where applicable, mediastinal and retroperitoneal areas. Non-nodal lesions include those in solid organs (eg, liver, spleen, kidneys, lungs), GI involvement, cutaneous lesions, or those noted on palpation. Nonmeasured lesions: Any disease not selected as measured, dominant disease and truly assessable disease should be considered not measured. These sites include any nodes, nodal masses, and extranodal sites not selected as dominant or measurable or that do not meet the requirements for measurability but are still considered abnormal, as well as truly assessable disease, which is any site of suspected disease that would be difficult to follow quantitatively with measurement, including pleural effusions, ascites, bone lesions, leptomeningeal disease, abdominal masses, and other lesions that cannot be confirmed and followed by imaging. In Waldeyer's ring or in extranodal sites (eg, GI tract, liver, bone marrow), FDG uptake may be greater than in the mediastinum with complete metabolic response, but should be no higher than surrounding normal physiologic uptake (eg, with marrow activation as a result of chemotherapy or myeloid growth factors).

†PET 5PS: 1, no uptake above background; 2, uptake ≤ mediastinum; 3, uptake > mediastinum but ≤ liver; 4, uptake moderately > liver; 5, uptake markedly higher than liver and/or new lesions; X, new areas of uptake unlikely to be related to lymphoma.

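### Eligibility requires no measurable or FDG-avid disease although ORR is primary, and the plan does not say which Lugano column decides response; one patient unable to respond would cost about 6 points of power

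*Combined protocol and SAP*

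**What the plan says.** Section 11.1 asks for histologically confirmed relapsed or refractory follicular lymphoma and at least one of six treatment indications. Three of the six set no lesion requirement: a B-symptom, lymphoma-related cytopenia, and "pleural or peritoneal serous effusions". Neither section 11.1 nor section 11.2 mentions measurable, assessable or FDG-avid disease.

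Section 15.1 lists "Measurable lesion assessment on CT scan of neck, chest, abdomen and pelvis" among the screening procedures, with no minimum size or number of lesions attached. FDG-PET is mandatory at baseline, after cycle 3 and at the end of induction (section 10.1).

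Section 9.3 defines the primary endpoint as investigator-assessed response after cycle 6 by Lugano 2014. Patients with no tumor assessment after the start of therapy count as non-responders. Section 17.3 analyses everyone who received at least one dose.

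Appendix C prints a PET-CT column and a CT column. CT partial response needs at least a 50% "decrease in SPD of up to 6 target measurable nodes and extranodal sites". The notes to the table place among non-measured disease the sites that are hard to follow quantitatively, "including pleural effusions, ascites, bone lesions, leptomeningeal disease, abdominal masses, and other lesions that cannot be confirmed and followed by imaging". No section says which column governs ORR.

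**The concern.** A single-arm trial with response as its primary endpoint normally requires baseline disease on which a response can be scored. Here a patient can satisfy every written criterion with nothing but an effusion, or marrow disease causing cytopenia. If the CT column were applied, partial response would be closed to that patient, who would nevertheless stay in the denominator of 43.

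The design has little room for this. It needs 29 responses in 43, with attained power only just above 80%. What is at stake is a false-negative result, including an unwarranted stop after stage 1. There is also an avoidable ambiguity in how such a patient would be scored.

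**Working it through.** **Inputs from section 17.1**
- Null rate 0.55 and one-sided alternative 0.75.
- Simon optimal two-stage design.
- Stage 1: "If there are 9 or fewer responses in these 15 patients, the study will be stopped".
- Stage 2 adds 28 patients. The null hypothesis is rejected at 29 or more responses in 43.
- Stated type I error 5% and power 80%.

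**Assumptions, not in the documents**
- k = number of treated patients without measurable disease, taken as 0 to 3.
- q = response probability of such a patient, taken from 0 to 0.75.

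**Step 1. Reproduce the plan's figures.** With X1 ~ Bin(15, p) and X2 ~ Bin(28, p), the probability of rejecting is the sum over x = 10 to 15 of P(X1 = x) × P(X2 ≥ 29 − x).
- At p = 0.55: 0.0496.
- At p = 0.75: 0.8048.

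The stated 5% and 80% are confirmed.

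**Step 2. One patient with q = 0, the others at 0.75.**
- In stage 1, X1 becomes Bin(14, 0.75). The chance of passing stage 1 falls from 0.852 to 0.742, and overall power is 0.6884, a loss of 11.6 points.
- In stage 2, X2 becomes Bin(27, 0.75). Power is 0.7750, a loss of 3.0 points.
- Averaged over position: (15/43) × 0.6884 + (28/43) × 0.7750 = 0.7448, a loss of 6.0 points.

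**Step 3. More than one such patient.** With k fixed non-responders, the number j falling in stage 1 is hypergeometric, with probability C(15, j) × C(28, k − j) / C(43, k). Averaging over j:

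| k | Average power | Further loss (points) |
|---|---|---|
| 0 | 80.5% | – |
| 1 | 74.5% | 6.0 |
| 2 | 67.3% | 7.2 |
| 3 | 59.0% | 8.3 |

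**Step 4. Relax q = 0.** For one patient, power is linear in q. It equals 0.7448 at q = 0 and 0.8048 at q = 0.75, so the loss is 6.0 × (1 − q/0.75) points.
- q = 0.375: loss 3.0 points, power 77.5%.
- q = 0.75: no loss.

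**Step 5. Direction of the error.** With one certain non-responder and the others at the null rate of 0.55, the rejection probability falls from 4.96% to 3.3%.

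**Step 6. Is q = 0 realistic under Appendix C?**
- CT partial response: needs target measurable lesions, so it is not available.
- CT complete response: non-measured lesions must be absent, enlarged organs back to normal and marrow normal. It remains possible when an effusion or marrow disease clears.
- PET-CT complete metabolic response: score 1 to 3, with or without a residual mass. It remains possible.
- PET-CT partial metabolic response: reduced uptake with residual masses of any size. No CT-measurable target is needed.

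So q = 0 is a worst case, not what the criteria as a whole imply.

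**The case against.** The strongest reply is that the gap will rarely matter. B-symptoms, cytopenia and effusions are reasons to treat, added to a histologically confirmed relapse, and they do not imply that measurable nodes are absent. Biopsy material goes to compulsory central review before treatment. A CT measurement of lesions is part of screening, so the authors evidently expected measurable disease. The documents give no count of patients without it, and zero is compatible with them. Mandatory PET offers a second route to response. All of this stands, and it limits the size of the point.

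Two things remain. PET helps only if there is avid disease at baseline, which is not required either, and only if the PET-CT column may decide ORR, which is not stated. The synopsis also wavers on baseline PET: it calls it recommended for grade 3A before calling it mandatory.

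A reader might infer three stronger things that the documents do not support:
- **Such a patient is an automatic non-responder.** The only rule of that kind, in section 9.3, covers patients with no post-baseline tumor assessment.
- **Every such patient costs about 6 points.** That figure is the average for the first only. The loss depends on stage and on q, and it grows with k.
- **The gap endangers the type I error.** Counting these patients as non-responders lowers alpha. Alpha would rise (to 6.3% with one patient) only if a patient without evaluable baseline disease were always scored a responder, and nothing in the plan directs that.

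**Conclusion.** The omission is real: no criterion secures a lesion on which the primary endpoint can be scored, and the governing response column is unnamed. Its cost is an upper bound. One patient with no chance of response would take power from 80.5% to about 74.5%, within 68.8% to 77.5% according to stage; two would take it to 67.3% and three to 59.0%. These figures assume that such patients are enrolled, that they cannot respond by any route, and that all others respond at 75%. The first two assumptions have no support in the documents beyond being possible, and the loss vanishes as q nears 0.75. Under the same assumptions the error is conservative, so the risk is of missing a real effect. This is an inexpensive improvement, not a flaw that invalidates the design.

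**What to change.** Add to section 11.1 and the synopsis a criterion of at least one lesion at baseline that is CT-measurable or FDG-avid by Appendix C. In section 9.3, state which Appendix C column decides ORR, and align the synopsis wording on baseline PET with section 10.1.

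The cost is small. A few rare patients become ineligible, and the scans needed to apply the criterion are already mandatory at screening. The sample size and decision rule do not change.

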## 11.2. Exclusion criteria

- Grade 3b follicular non-Hodgkin's lymphoma or evidence of transformation to high-grade non-Hodgkin's lymphoma.
- Central nervous system or leptomeningeal involvement by lymphoma.
- Major surgery (excluding any lymph node biopsy) within 28 days prior to signing informed consent.
- Seropositivity for HBV or evidence of active infection (HBsAg positivity, or HBsAg negativity with positive anti-HBs/anti-HBc and detectable viral DNA load); if viral load is negative or undetectable, the patient is eligible, provided their HBsAg negativity.
- Positive viral HCV RNA.
- Seropositivity for HIV, regardless of viral load.
- Known history of drug induced liver injury, chronic active hepatitis C (HCV), chronic active hepatitis B (HBV), alcoholic liver disease, non-alcoholic steatohepatitis, primary biliary cirrhosis, on-going extra-hepatic obstruction caused by cholelithiasis, cirrhosis of the liver or portal hypertension.
- Known history of drug induced pneumonitis.
- On-going inflammatory bowel disease.
- On-going alcohol or drug addiction.
- Life expectancy lower than 6 months.
- Prior history of malignancies, other than follicular lymphoma, unless the patient has been free for at least 10 years (exceptions: localized non-melanoma skin cancer and carcinoma in situ of the cervix).
- Any of the following laboratory abnormalities: liver enzymes (AST/SGOT and/or ALT/SGPT) > 2.5-fold the upper limit of normal (except of liver involvement by lymphoma); total bilirubin > 1.5 mg/dL (except for patients with known Gilbert's disease or biliary tree compression by lymphoma masses); creatinine clearance < 30 mL/min.
- Uncontrolled intercurrent illness.
- Known hypersensitivity or allergy to murine products or to any of the medicaments under investigation.
- Pregnancy or breastfeeding, or unwillingness to comply with adequate contraception.
- Any serious medical condition, laboratory abnormality or psychiatric illness that would prevent the patient from signing the informed consent or which may place the patient at unacceptable risk if participating in the study.
- Any evidence of ongoing bacterial, viral and fungal infection.
- Known hypersensitivity to the active substances or to any of the excipients.
- Concomitant participation into another trial planning experimental therapy.

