### **13.6. Patients HBV positive**

Not included in this study as per inclusion/exclusion criteria.

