#### **Obinutuzumab**

**WARNING: HEPATITIS B VIRUS REACTIVATION and PROGRESSIVE MULTIFOCAL LEUKOENCEPHALOPATHY**

- Hepatitis B Virus (HBV) reactivation, in some cases resulting in fulminant hepatitis, hepatic failure, and death, can occur in patients receiving CD20-directed cytolytic antibodies, including obinutuzumab. Screen all patients for HBV infection before treatment initiation. Monitor HBV-positive patients during and after treatment with obinutuzumab. Discontinue obinutuzumab and concomitant medications in the event of HBV reactivation (see *paragraphs 13.5 and 13.12*).
- Progressive Multifocal Leukoencephalopathy (PML) including fatal PML, can occur in patients receiving obinutuzumab (see *paragraphs 13.5 and 13.12*).

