### **Infections**

Fatal and serious bacterial, fungal, and new or reactivated viral infections can occur during and following obinutuzumab therapy. Patients with a history of recurring or chronic infections may be at increased risk of infection.

A “black-box” warning for obinutuzumab states that reactivation of hepatitis B as well as other serious viral infections (e.g., infections caused by cytomegalovirus, Varicella zoster virus, herpes simplex virus, JC virus, and HCV) that were new, reactivated, or exacerbated have been reported with the B cell-depleting antibody rituximab mainly in patients who had received the drug in combination with chemotherapy or as part of a hematopoietic SCT. The risk of such infections with obinutuzumab is unknown.

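### Section 11.2 admits HBsAg-negative, antibody-positive patients with undetectable HBV DNA, but the protocol gives them no scheduled HBV test after screening and does not say whether its HBV monitoring warning covers them

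*Combined protocol and SAP*

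**What the plan says.** Four parts of the protocol bear on hepatitis B.

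- **Eligibility (section 11.2, same text in the synopsis).** The exclusion begins "Seropositivity for HBV or evidence of active infection (HBsAg positivity, or HBsAg negativity with positive anti-HBs/anti-HBc and detectable viral DNA load". After the parenthesis it continues: "if viral load is negative or undetectable, the patient is eligible, provided their HBsAg negativity". A separate exclusion covers a known history of chronic active hepatitis B.
- **Management (section 13.6, on HBV-positive patients).** The whole section reads "Not included in this study as per inclusion/exclusion criteria".
- **Warning (section 13.11, obinutuzumab).** After asking for HBV screening of all patients, it says "Monitor HBV-positive patients during and after treatment with obinutuzumab" and then "Discontinue obinutuzumab and concomitant medications in the event of HBV reactivation". It refers the reader to sections 13.5 and 13.12.
- **Testing (sections 15.1 and 15.9).** The screening list includes "Viral tests including HIV, HBsAg, HBsAb, HBcAb, HBV DNA and HCV". In the schedule of assessments the virology row carries one mark, in the screening column. The synopsis likewise places hepatitis serology at enrolment.

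**The concern.** The warning is an instruction to monitor, and its discontinuation rule depends on recognising a reactivation. Section 11.2 lets in patients with serological evidence of HBV, section 13.6 tells sites that HBV-positive patients are absent, and the schedule asks for no HBV test once treatment has started. A site that follows the visit lists exactly would test these patients once and not again.

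This is a patient-safety matter. No effect on the response-rate endpoint or on the two-stage design is claimed. The protocol itself treats the risk as serious: section 13.11 says reactivation under CD20-directed antibodies can lead to liver failure and death, and Appendix F lists 9 serious hepatitis B reactivations in a pool of 3745 patients.

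**Working it through.** No statistical calculation applies, and the plan gives no figure to reproduce. The check sets the sections side by side.

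**1. Who is admitted under 11.2.** Taking the criterion pattern by pattern:

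| HBsAg | Anti-HBs/anti-HBc | HBV DNA | Outcome |
|---|---|---|---|
| Positive | any | any | Excluded |
| Negative | Positive | Detectable | Excluded |
| Negative | Positive | Negative or undetectable | Opening words suggest exclusion; final clause admits |
| Negative | Negative | Negative or undetectable | Eligible |

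The third row is the group at issue. The parenthesis does not list it and the final clause makes it eligible. The exclusion for chronic active hepatitis B does not remove it.

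**2. Where the warning's cross-references lead.** Section 13.5 covers infections in general, PJP, CMV, neutropenia, thrombocytopenia, tumour lysis and cardiac disease. It does not mention HBV. Section 13.12, in its obinutuzumab part on infections, mentions "reactivation of hepatitis B as well as other serious viral infections" as events reported with rituximab. It gives no test, interval, duration or action.

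**3. What is scheduled.** Counting from sections 15.1 to 15.9:

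- HBV serology or HBV DNA at screening: 1 time point.
- HBV serology or HBV DNA in induction, restaging, end of induction, end of treatment, early withdrawal, maintenance, follow-up and survival follow-up: 0 time points.
- No schedule footnote adds a later HBV test. The visit lists for maintenance and follow-up (15.5, 15.6) name clinical laboratory evaluations without itemising them, but the virology row is blank in those columns.
- By contrast, CMV is tested every two weeks from the first day of cycle 1, and 13.12 attaches an action rule to it.

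**4. Length of exposure without a scheduled test.** Induction is 6 cycles × 28 days = 168 days, or 168/365.25 ≈ 0.46 years. Maintenance is up to 2 years. The total is 0.46 + 2 = 2.46, about 2.5 years of obinutuzumab. The warning also asks for monitoring after treatment, so the two-year follow-up is affected too.

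**5. The two readings of HBV-positive.** The protocol does not define the term.

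- *Any HBV seropositivity.* Section 13.6 then contradicts 11.2, because such patients are included. The 13.11 warning covers them, with no scheduled test behind it.
- *Only patients barred by 11.2.* Section 13.6 is then consistent with 11.2, but the monitoring instruction applies to nobody enrolled, and the antibody-positive, DNA-negative patients fall outside every HBV provision after screening.

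Neither reading gives the admitted group a scheduled HBV test.

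**The case against.** The other side has several fair points.

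- **The criterion can be applied.** Section 11.2 is clumsy, but every serology and DNA pattern can be resolved, and screening collects all the inputs. This stands. A reader might infer that eligibility is undecidable, and the text does not support that.
- **Section 13.6 need not conflict with 11.2.** It points to the eligibility criteria, so it can be read as covering only excluded patients. This stands as a possible reading, and no section says that the warning in 13.11 means antibody-positive, DNA-negative patients. It changes the problem from a contradiction to an omission and does not close the gap.
- **The warning can still be followed.** A reader might infer that the monitoring is impossible to carry out. That goes too far: section 20.2 lets investigators run tests outside the schedule when the patient's medical care requires it. But this is an exception to a rule that otherwise needs prior written approval, and section 13.6 gives sites little reason to use it.
- **Viral monitoring does not stop at screening.** This is correct, since CMV is repeated. The gap concerns the HBV tests.
- **There is a partial safety net.** AST, ALT and bilirubin are measured before each induction cycle, on days 8 and 15 of cycle 1, and at end of treatment and early withdrawal. The chemistry row is also marked in maintenance and follow-up. Combined transaminase and bilirubin elevation must be reported within 24 hours (adverse events of special interest, section 16.3). This stands, but the signal is indirect. Section 13.11 reports fatal or serious hepatotoxicity in 16% to 18% of idelalisib-treated patients, so a transaminase rise alone would not identify HBV reactivation, which is the stated trigger for discontinuation.
- **The investigator's brochures may say more.** The protocol refers to them, and they were not available for this review.

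**Conclusion.** The point holds in this form: the protocol admits HBsAg-negative, antibody-positive patients with undetectable HBV DNA, does not define the HBV-positive patients its warning concerns, and schedules HBV testing at 1 time point before treatment and 0 afterwards. The period without a scheduled HBV test is up to about 2.5 years of obinutuzumab plus follow-up.

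The conclusion rests on the virology row as it appears in the extracted schedule, supported by the visit lists, and on the final clause of 11.2 governing eligibility. How many such patients would enrol is not stated. The Appendix F count, 9/3745 ≈ 0.24%, cannot be applied to them because the serology of that pool is not given.

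The documents do not show that HBV monitoring is forbidden or impossible, or that there is no indirect signal of liver injury. The sections should be reconciled before sites rely on them.

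**What to change.** Define HBV-positive once, stating which combinations of HBsAg, antibodies and HBV DNA it covers. Then make these places agree with that definition and with each other:

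- the HBV exclusion in the synopsis and section 11.2, including its opening words;
- section 13.6;
- the warning in 13.11 and the two sections it cites, 13.5 and 13.12, so that the references lead to the procedure they imply;
- the visit lists starting at 15.1 and the virology row in 15.9.

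The aim is that the patients admitted and the HBV monitoring the protocol requires for them match. Whether that is done through eligibility, monitoring or both is for the sponsor's clinical team, and no rule is proposed here. The cost is a wording amendment and possibly one schedule row. Sample size and analysis are unchanged unless the eligible population changes.
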